## 8.2 Treatment schedule

The treatment schedule includes a pre-operative assessment, the CI surgery, the first activation visit and well as the 3 months' post-operative visit. The CT scans before and after surgery are part of the clinical routine test battery.

Procedure	Pre-op	Surgery	First Activation	3 months post-op
Informed Consent	X			
Demographics, Medical & Hearing History	X			
Surgical questionnaire		X		
Voltage tomography and impedance matrix		X (after electrode insertion)	X	X
Auto NRT thresholds		X (after electrode insertion)	X	X
CT/DVT Scan	X	X (after electrode insertion, may be done after surgery)		
(S)AE, ADE, DD		X	X	X
Protocol deviations		X	X	X

The Demographic, Medical and Hearing History is part of the pre-op assessment. The surgical questionnaire applies after the surgery to collect information on insertion related events and

the name of the surgeon who has inserted the electrode array. The Auto NRT thresholds, the voltage tomography and impedance matrix applies during surgery as well as during the first activation session and three months after surgery. An active follow-up on the occurrence of (S)AE, ADE, DD applies. Protocol Deviations will be documented as soon as possible after occurrence. The acceptable visit window tolerance is +/-1 month.

## **8.3 Subjects**

### **8.3.1 Inclusion Criteria**

1. Candidate for cochlear implantation with the CI532 or CI512 device
2. 18 years of age or older at the time of enrolment
3. Normal cochlea anatomy, established via pre-operative CT
4. Willingness to participate in and to comply with all requirements of the protocol

### **8.3.2 Exclusion Criteria**

1. Prior cochlear implantation in the ear to be implanted
2. Ossification or any other cochlear anomaly that might prevent complete insertion of the electrode array
3. Abnormal cochlear anatomy on pre-operative CT or MRI imaging
4. Additional handicaps that would prevent participation in evaluations
5. Pregnant and breast feeding women, prisoners, or anyone in custody
6. Unrealistic expectations on the part of the subject, regarding the possible benefits, risks and limitations that are inherent to the procedure

### **8.3.3 Criteria and procedures for subject's withdrawal or discontinuation**

Subjects can decide to withdraw from the investigation without indicating any reasons. The investigator may decide to discontinue a patient due to major non-compliance with the CIP requirements (e.g. visit schedule not met). The investigator may also decide to discontinue a patient's involvement in the study for several reasons, including the subject not reasonably following the visit schedule described in Chapter 8.2, the subject no longer satisfying the Inclusion/Exclusion criteria (e.g., subject becomes pregnant during the study or develops a handicap that prevents the ability to sufficiently perform the tests) or if there are any reportable (S)AE, ADE, DD. If a subject withdraws or is withdrawn from the study, that subject will still be provided with routine CI aftercare and maintenance at the investigational sites as part of the clinical routine.

### **8.3.4 Point of enrolment**

Subjects who satisfy the inclusion criteria will be provided with a clear explanation of the Patient Informed Consent (PIC) with sufficient time for discussion and clarification to ensure the patient understands the requirements and expectations. Subjects are enrolled into the clinical investigation when they have signed the Informed Consent Form.

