The CT/DVT imaging before and after surgery and the CSEP measurements during and after surgery is part of the clinical routine in CI treatment and patients will be selected who follow this clinical routine.

In addition, the measurements, CT/DVT scans and classifications will be de-identified and stored in a database to support the further development and validation of algorithms. Those insertions showing the presence of anomalous properties will be excluded from the dataset that is presented to the candidate algorithm but will be included in this database. To allow for the exclusion of these insertions an additional 9 subjects are added to the study.

Depending on the recommended practice in the clinics the measures of surgeries performed by experienced and unexperienced surgeons will be collected. For retracement the name of the inserting surgeon is labelled on the surgical questionnaire.

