### 8.3.7 Number of subjects required to be included in the clinical investigation

154, assuming that 9 recipients will not be suitable for the evaluation of the algorithm due to the occurrence of an insertion anomaly.

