### 8.4.1 Pre-Operative

The patient will be provided the Patient Informed Consent (PIC) to review, to discuss with the principal investigator of the study and to sign. One version of the signed PIC will be collected.

Within the clinical routine, the CT/DVT Scan will be performed along with the collection of standard medical and hearing history.

Demographics, Medical and Hearing History will be completed as part of the pre-operative assessment.

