This entails that the false positive rate is no more than 2%, or that no more than 1 out of 50 insertions with normal position will be indicated as anomalous, and potentially receive medical imaging just to reveal that the insertion is normal. Assuming the incidence of tip fold-overs to be around 4% for pre-curved arrays, the 98% specificity will provide a positive predictive value of over 60% which meets the target positive predictive value from section 3.

In conclusion, 154 implantations are required.

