2.1 Overview

A total of 154 patients will be assessed in the statistical analysis of the data. This will serve to collect a representative sample of the variability of surgical techniques across clinics and surgeons. The confidence interval to be used in the analyses will be a 90% two-tailed. This confidence interval was deemed to be satisfactory due to the exploratory nature of the study. The statistical analyses conducted for the primary and secondary objectives will lead to the endpoints of the study.

The statistical analysis will be conducted by [REDACTED], Cochlear).

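### The stated 89% chance of at least 145 normal insertions assumes that all 154 subjects yield an evaluable insertion; the plan counts subjects at consent and allows for no loss except 9 anomalies.

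*Protocol*

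**What the plan says.** Protocol 8.3.4 defines the point of enrolment: "Subjects are enrolled into the clinical investigation when they have signed the Informed Consent Form". Section 8.3.7 gives the number of subjects to be included as "154, assuming that 9 recipients will not be suitable for the evaluation of the algorithm due to the occurrence of an insertion anomaly". Section 8.1 gives the same reason for the margin: "To allow for the exclusion of these insertions an additional 9 subjects are added to the study".

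The same figure then appears in two other units. Protocol 9.1 ends with "In conclusion, 154 implantations are required", and SAP 2.1 states "A total of 154 patients will be assessed in the statistical analysis of the data".

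Protocol 9.1 and SAP 2.2 put the chance of 9 or fewer tip fold-overs in 154 at 89%, leaving at least 145 normal insertions. SAP 3.1 repeats the 89% as the chance of having at least 145 normal patients, and says the specificity target is reached if all of at least 145 are classified correctly.

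Losses are foreseen. Protocol 8.3.3 lets subjects withdraw without a reason and lets the investigator discontinue them. SAP section 4 says that where data are missing or spurious, or a patient drops out, whatever remains is analysed. SAP section 6 removes only confirmed anomalies. Neither document gives a loss rate, a replacement rule or a definition of screen failure.

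**The concern.** One number serves as subjects enrolled, implantations performed and patients analysed, and nothing in the text makes the three equal. A subject can be enrolled and still contribute no negative case: by failing eligibility, withdrawing before surgery, receiving a different array, or having no usable intra-operative matrix or post-operative scan. The scan matters as much as the matrix, because without it an insertion cannot be classified as normal.

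The 9 spare subjects are already committed to anomalies. What is at stake is the stated assurance of reaching 145 normal insertions, the number on which the plan's all-correct criterion rests.

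**Working it through.** **Inputs from the documents.** Number of subjects 154 (Protocol 8.3.7, 9.1). Required normal insertions 145 (Protocol 9.1, SAP 2.2). Anomaly rate from SAP 2.2 and Appendix A: (5 + 4) / (0.48 × 303 + 72) = 9 / 217.44 = 0.04139. Two-sided 90% Clopper-Pearson interval (SAP 2.1, 2.2).

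**Inputs assumed.** The number or rate of losses, and that a loss is unrelated to whether the insertion is anomalous. The documents give neither.

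**The plan's own figures.** With X ~ Binomial(154, 0.04139), P(X ≤ 9) = 0.8925, which is the stated 89%. With all n correct, the lower bound is 0.05^(1/n); at n = 145 this is 0.9796, against the printed 97.97%. That small gap plays no part here.

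**Why the margin is thin.** The expected number of normal insertions with no loss is 154 × (1 − 0.04139) = 147.6, under three cases above 145.

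**Fixed losses.** If L of the 154 are unusable, N = 154 − L remain, and at least 145 normal insertions requires X ≤ N − 145 with X ~ Binomial(N, 0.04139).

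| Lost (assumed) | Evaluable N | Anomalies tolerated | P(at least 145 normal) |
|---|---|---|---|
| 0 | 154 | 9 | 0.8925 |
| 1 | 153 | 8 | 0.8151 |
| 2 | 152 | 7 | 0.7052 |
| 3 | 151 | 6 | 0.5654 |
| 5 | 149 | 4 | 0.2575 |
| 10 or more | 144 or fewer | not attainable | 0 |

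**Random losses.** If each subject is lost with probability d, each yields a normal evaluable insertion with probability (1 − 0.04139)(1 − d). For d = 1% this is 0.9490, and P(at least 145 of 154) = 0.739. For d = 2%, 3% and 5% the results are 0.543, 0.355 and 0.110.

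**Effect on the confidence bound.** With all cases correct, 0.05^(1/145) = 0.97955 and 0.05^(1/140) = 0.97883, a difference of 0.07 percentage points. With 5 lost, P(X ≤ 9) for N = 149 is 0.909, so at least 140 normal insertions would still be available with about 91% probability.

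**The case against.** The best defence has four parts.

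- **The 89% is correct for what it describes:** at most 9 fold-overs given 154 insertions. That stands as arithmetic. But Protocol 9.1 carries it straight on to at least 145 normal insertions, and SAP 3.1 quotes it as the chance of having that many patients. There it acts as a yield, and its condition is not stated.
- **The sponsor may mean to recruit until 154 are implanted,** in which case losses before surgery use no place. A reader might infer the opposite, that recruitment closes at 154 signatures. The documents do not say that. They do not state the sponsor-friendly reading either: 8.3.7 counts subjects, 8.3.8 ties that number to the enrolment period, and 8.3.4 places enrolment at consent.
- **Drop-out need not harm the primary analysis.** This stands for drop-out after the post-operative scan. The primary endpoint needs only the intra-operative measurements and that scan, and SAP section 4 retains collected data. Later drop-out affects only the activation and 3-month analyses.
- **The study is exploratory and aims at approximately 98%.** This also stands: falling a few cases short of 145 barely moves the bound, so the scenarios do not show that the specificity conclusion fails.

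A further tempting reading is that consent precedes the CT that decides eligibility. The documents do not settle this. Section 8.3.4 offers consent to subjects who already meet the inclusion criteria, one of which is "Normal cochlea anatomy, established via pre-operative CT". Section 8.4.1 describes consent first and then says "Within the clinical routine, the CT/DVT Scan will be performed along with the collection of standard medical and hearing history", without fixing a sequence. The treatment schedule in 8.2 puts both in the pre-operative column. This is an inconsistency to reconcile. The main point does not depend on it, because consent precedes surgery either way.

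**Conclusion.** The point holds as a defect in a stated figure and in an undefined count. The 89% is valid only for 154 implanted subjects, each with a usable intra-operative matrix and post-operative scan. On the plan's own fold-over model, one unusable case takes it to 82% and three to 57%. These values rest on assumed losses, since the documents give no rate, and on losses being independent of anomaly status.

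The damage is to the assurance of reaching 145, not to the precision of the specificity estimate. The correction is worth making because the 89% appears in three places and supports the plan's all-correct criterion.

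**What to change.** 1. In Protocol 9.1, SAP 2.2 and SAP 3.1, state that the 89% is conditional on 154 evaluable insertions. Give the scenario values beside it: 82%, 71%, 57% and 26% for 1, 2, 3 and 5 unusable cases, and 74% for a 1% random loss. Note that the all-correct bound is 97.96% at 145 and 97.88% at 140.
2. In Protocol 8.3.4 and 8.3.7, state that subjects who consent but fail eligibility, withdraw before surgery or receive another array are screen failures and do not count towards 154.
3. Leave losses after implantation (no usable matrix or scan) to the restated figure in item 1. Replacing those subjects would need implantations beyond the 154.
4. Reconcile 8.3.4 with 8.4.1 on whether the CT criterion is met before consent.

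The cost is amendment wording and a few extra consents to replace screen failures. Item 2 adds no implantations beyond the 154 planned. The stated assurance becomes less favourable, but it carries its condition.

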### **8.3.5 Total expected duration of the clinical investigation**

19 months

### **8.3.6 Expected duration of each subject's participation**

3 months

### 8.3.7 Number of subjects required to be included in the clinical investigation

154, assuming that 9 recipients will not be suitable for the evaluation of the algorithm due to the occurrence of an insertion anomaly.

### 8.3.8 Estimated time needed to select this number (i.e. enrolment period)

16 months

## 8.4 Procedures

The procedure of this clinical investigation follows the clinical routine battery of CI treatment by implementing a pre-operative visit, the surgery, the first activation as well as a 3 months' post-operative visit.

Protocol deviations, (S)AE, ADE, DD will be actively collected and reported according to national and regional requirements at each study visit after the patient has signed the PIC.

### 8.4.1 Pre-Operative

The patient will be provided the Patient Informed Consent (PIC) to review, to discuss with the principal investigator of the study and to sign. One version of the signed PIC will be collected.

Within the clinical routine, the CT/DVT Scan will be performed along with the collection of standard medical and hearing history.

Demographics, Medical and Hearing History will be completed as part of the pre-operative assessment.

### 8.4.2 Surgery

After electrode array insertion, the extra-cochlear electrode lead is placed and the plate electrode is covered by skin flap. The NRT, trans-impedance and voltage measurements are performed using CSEP. The CSEP measurements take approximately 11 minutes for Auto-NRT with conditioning on 22 electrodes and 1 minute for trans-impedance and voltage measurements. Since Auto-NRT is part of the clinical routine, the additional time effort for this study is 1 minute.

The following sequence applies:

1. Auto NRT with conditioning on 22 electrodes
2. Trans-impedance and voltage measurements

The CT/DVT scan of the intra-cochlear electrode array positioning will be conducted as part of the clinical routine battery.

Within the surgical questionnaire the number of surgeries of the implanting surgeon, insertion related events as well as the corrective actions (if applicable) are documented. This information will be entered into the corresponding CRF after review by the surgeon.

In case the electrode array placement needs to be corrected as part of the clinical and surgical routine, the following workflow maintains:

1. If not already done as described before: Run the trans-impedance and voltage measurements before removing the electrode array.
2. Correct the electrode array placement as per normal clinical routine.
3. After successful reinsertion / corrective action of the position of the electrode array, run the Auto-NRT, trans-impedance and voltage measurements again.

The intra-operative measures with CSEP will be exported as cdx/csv files and transferred in an anonymized form to Cochlear.

An active follow-up on the occurrence of (S)AE, ADE, DD applies. Protocol Deviations (if applicable) will be documented as soon as possible after occurrence.

### 8.4.3 First Activation

At the end of the first activation CSEP 5 will be used to perform an NRT threshold measurement on 22 electrodes followed by the trans-impedance and intra-cochlear voltage measurement.

In some clinics, it is part of the clinical routine to measure NRT on 22 electrodes at the start of the first activation visit. These clinics should continue following routine practice and only perform the trans-impedance and voltage measurements at the conclusion of the first activation visit. The effort of those measures may take approximately 12 minutes.

Following the conclusion of the clinical session the measures with CSEP for this session will be exported as cdx/csv file and transferred in an anonymized form to Cochlear.

An active follow-up on the occurrence of events applies. Protocol Deviations (if applicable) will be documented as soon as possible after occurrence.

### 8.4.4 3 months post-op

At the end of the first activation CSEP 5 will be used to perform an NRT threshold measurement on 22 electrodes followed by the trans-impedance and intra-cochlear voltage measurement. The effort of those measures may take approximately 12 minutes.

Following the conclusion of the clinical session the measures with CSEP for this session will be exported as cdx/csv file and transferred in an anonymized form to Cochlear.

An active follow-up on the occurrence of events applies. Protocol Deviations (if applicable) will be documented as soon as possible after occurrence.

## 8.5 Monitoring Plan

The sponsor will appoint a study monitor to perform regular visits at the study site, as defined in the Monitoring Plan. Prior to the first subject enrolment, an initiation visit will be performed by the clinical project manager or delegate and the study monitor ensuring that assigned study personnel are familiar with this Clinical Investigation Plan and procedures and device handling, trained in Good Clinical Practice (GCP) compliance, eCRF completion, event reporting, and maintenance of study related documentation.

The study monitor will ensure compliance with the clinical investigation plan and EN ISO 14155, accurate data recording on the eCRFs, will raise data clarifications, will monitor recruitment rates and adherence to follow-up schedules. The study monitor will also check the upkeep of the investigator file. The investigator shall permit and assist the study monitor to carry out verification of completed eCRFs against data in the source documents.

Source documents are defined as any printed, optical or electronic document containing source data (hospital records, audiograms, speech test results, laboratory notes, device accountability records, radiographs, records kept at the investigational site) necessary for the reconstruction and evaluation of the clinical investigation. The extent of source data verification is defined in the Monitoring Plan. The investigator shall provide all requested documentation in a timely and organized manner.

The study monitor shall inform the sponsor about any problems relating to facilities, technical equipment or medical staff at the study site.

The study monitor shall provide the clinical project manager with written reports, after each visit or contact with the investigational site.

The investigator has to inform the sponsor about any additional local requirements that may impact the work of a monitor especially if access to source data may be limited by local

regulations. This is to ensure any necessary action to be taken before the study start to allow proper monitoring according to the EN ISO 14155 Standard.

## 9 Statistical Considerations

### 9.1 Sample Size Calculation

An in-depth description of the statistical characterisation and correlation will be part of the Statistical Analysis Plan. Final statistical analysis will be conducted on a clean and complete database after database closure.

The candidate algorithm provides the ability to detect gross electrode position anomalies (eg. tip fold-over or electrode not in the cochlea). It provides binary outputs; a value of zero (negative result) or a value of one (positive result). A value of zero indicates that the algorithm concluded that an anomalous position has not occurred and the value of one indicates that the algorithm concluded that an anomalous position has occurred. To be useful as a tool that can replace routine use of X-rays and CT scans, the algorithm is required to have a minimal false positive rate. To ensure that this expectation is reasonably fulfilled, the 98% specificity target is set to be the lower bound of the 90% binomial confidence interval for the specificity of the algorithm. An iterative approach was adopted to estimate the required patient sample size which takes into account the likelihood of anomalous position events. It was assumed that the occurrence of a tip fold-over (the principal form of position anomaly under consideration) follows a binomial distribution with a positive probability of around 4% based on the weighted average percentage for tip fold-overs in pre-curved arrays reported by Grolman et al. 2009 and Zuniga et al. 2016. Using the Clopper-Pearson method a sample size of 154 was selected, which gives an 89% chance of 9 or less tip fold-overs taking place, resulting in at least 145 'normal' insertions. If the algorithm correctly diagnoses all 145 insertions, the lower bound of the two-tailed 90% confidence interval for specificity will be 97.97% which is approximately 98%. In other words, if the algorithm correctly identifies all 145 cases as 'normal' then it can be concluded that its specificity is 98% or better with 90% confidence.

This entails that the false positive rate is no more than 2%, or that no more than 1 out of 50 insertions with normal position will be indicated as anomalous, and potentially receive medical imaging just to reveal that the insertion is normal. Assuming the incidence of tip fold-overs to be around 4% for pre-curved arrays, the 98% specificity will provide a positive predictive value of over 60% which meets the target positive predictive value from section 3.

In conclusion, 154 implantations are required.

### 9.2 Candidate algorithm exploration

To explore the specificity of the candidate algorithm it will be provided with the trans-impedance data collected at surgery, first activation and 3 months post-operatively for insertions that has been determined not to contain any anomalous electrode array position based on the CT Scans.

In each instance the result of the algorithm will be analysed to determine the specificity based on the amount of positive and negative results returned by the algorithm.

---

 For the sample size calculation, it is assumed that the sensitivity (true positive) of the candidate algorithm is 90%.

